9.10.7 REPORTING SERIOUS ADVERSE EVENTS

Any SAE will be reported to the Sponsor via telephone, fax, e-mail, or in person, within 24 hours of knowledge by the Investigator. This will be managed according to the Safety Management Monitoring Plan. The notification must be directed to:

SAEs must be reported to the IRB within 24 hours of site awareness.

9.10.8 SUSPECTED, UNEXPECTED, SERIOUS ADVERSE DRUG REACTIONS (SUSAR)

It is the responsibility of the sponsor to determine whether a reported SAE fits the classification of a SUSAR and to notify the investigator of their decision as soon as possible.

The investigator and sponsor are responsible for notifying regulatory agencies of fatal or life-threatening serious, unexpected ADRs (by telephone, facsimile transmission or in writing) as soon as possible, but no later than 7 calendar days after becoming aware of the information.

Additionally, within 8 days after having informed the agency(ies), a complete report must be submitted, including an assessment of the importance and implication of any findings.

It is the responsibility of the investigator and sponsor to report SAEs to the IRB responsible for the study following the local procedure. The task of reporting other SUSARs may be delegated to the pharmacovigilance provider.

9.10.9 OTHER SUSPECTED, UNEXPECTED, SERIOUS ADVERSE DRUG REACTIONS

The Sponsor is responsible for notifying regulatory agencies of all other suspected, unexpected, serious ADRs that are neither fatal nor life-threatening as soon as possible, but no later than 15 calendar days after becoming aware of the information.

It is the responsibility of the investigator and sponsor to report to the IRB responsible for the study all other suspected, unexpected, serious ADRs that are neither fatal nor life-threatening, as soon as possible, but no later than 15 calendar days after first knowledge by the Investigator. The task of reporting other SUSARs may be delegated to the pharmacovigilance provider.

9.10.10 REPORTING OF URGENT SAFETY ISSUES

The sponsor is required to inform the appropriate regulatory authorities and investigators and the investigator is responsible for informing the IRB, within 3 calendar days of the urgent safety issue.

9.10.11 REPORTING OTHER SERIOUS IMPORTANT MEDICAL EVENTS

Report when the event does not fit the other outcomes, but the event may jeopardize the subject and may require medical or surgical intervention (treatment) to prevent one of the other outcomes. Examples include allergic bronchospasm (a serious problem with breathing) requiring treatment in an emergency room, serious blood dyscrasias (blood disorders), or seizures/convulsions that do not result in hospitalization. The development of drug dependence or drug abuse would also be examples of medical events.

9.10.12 POTENTIAL CLASS SPECIFIC EVENTS

Based on FDA review of available data, there are potential safety concerns for the entire class of Mn containing MRI contrast agents. These include the possibilities of Mn retention in the brain, hypersensitivity reactions, lowering of seizure threshold, and transient changes in CV function.

Therefore, sponsor will submit a 7- or 15-day IND safety report for any emergent treatment of seizure, stroke, cerebral venous thrombosis, QTc above 480 msec, or QTc increase of 60 msec over baseline, regardless of assessment of causality.

9.10.13 REPORTABLE DISEASE

In the case a subject has or manifested any clinical signs characteristic of a reportable disease (e.g., tuberculosis, SARS-CoV-2) it is the responsibility of the Medical Director to notify the Public Health authorities within 48 hours after becoming aware of the information or per local guidelines.

Additional details can be found in the safety management plan.

9.11 COVID RESPONSE PLAN

9.11.1 COVID-19 RELATED RISKS AND RISK MITIGATION MEASURES

The following risks and risk mitigating measures apply to the time in which the study is conducted during the COVID-19 pandemic.

9.11.1.1 STUDY DRUG RELATED RISK

Against the background of the COVID-19 pandemic, the potential risk of a subject developing COVID-19 has been considered in terms of the risk-benefit evaluation. RVP-001 is not biologically active. Based on available non-clinical and clinical data (including class effects), it is considered that a subject would not be at increased risk of either becoming infected with SARS-CoV-2 or experiencing a more severe illness. That is, the study drug has no known immunomodulatory effect that would confer an increased risk to healthy subjects enrolled in the study.

9.11.1.2 GENERAL COVID-19 RELATED RISKS AND RISK MITIGATION MEASURES

General risk mitigation against COVID-19 will be implemented in accordance with Quotient's monitoring and prevention control measures.

The risk mitigation measures, where applicable, will be amended based on emerging government guidance.

9.11.1.3 COVID-19 VACCINE-RELATED RISK

Approved (including health authority conditional marketing authorization) COVID-19 vaccines e.g., killed, inactivated, peptide, deoxyribonucleic acid (DNA), and riboneucleic acid (RNA) vaccines may be permitted according to the investigator's discretion and as per local guidance.

Due to lack of biological activity of RVP-001, there is no perceived impact on the safety of the study subjects or on the study objectives for subjects who may receive these vaccines (either first, second, or booster doses). It is also very unlikely that administration of the study drug would interfere with COVID-19 vaccination response; however, no specific pre-clinical or clinical investigations have been conducted at this point with RVP-001.

The emerging safety and efficacy data from millions of vaccinated people indicate that these vaccines have an excellent safety and efficacy record. In the broader interests of society and to limit the extent of the global pandemic, it is important that subjects should receive a vaccine when it is offered to them.

9.12 SAFETY REVIEW COMMITTEE (SRC)

9.12.1 DECISION POINTS

The following in-study decisions will be made during this study:

- Dose selection for Cohorts 2 to 4.
- Progression from sentinel group to main group
- Changes to safety and/or PK time points, if there is reason to believe that the change might improve the quality of the data as a consequence of review of emerging data.

9.12.2 CRITERIA FOR DOSE DECISIONS

Cohorts will be dosed sequentially in an ascending fashion.

Following completion of each SAD cohort, a SRC will convene to review all available blinded safety, tolerability and available PK/exposure assessments up to Day 6 (120 hours) performed for each SAD cohort, and together with attempts to correlate exposure levels with observed AEs to evaluate progression to the next dose cohort.

The SRC will be comprised of the Principal Investigator at the clinical site and the Sponsor's medical personnel, at a minimum.

Criteria for Sentinel Dosing Decision(s)

For all cohorts following a sentinel design the decision to proceed with the main group will be made by the investigator, based on safety data until 24 hours post-dose of the last sentinel subject. The investigator will inform the sponsor of any safety concerns.

For additional details refer to Data Safety Monitoring Plan (DSMP).

10 STATISTICAL CONSIDERATIONS

10.1 POPULATIONS FOR ANALYSES

Populations and analysis sets will be determined for safety and PK after database lock using the criteria defined in the statistical analysis plan (SAP); the SAP will be signed off prior to database lock. The safety population and safety analysis set will be defined after database lock but prior to study unblinding; all other populations will be defined after database lock when the relevant data are available.

10.1.1 SAFETY POPULATION

The safety population will include all subjects who received at least 1 dose of RVP-001 or placebo.

The number of subjects who were included, who discontinued, and who completed the study will be tabulated. The primary reasons for discontinuation will be provided.

10.1.2 PHARMACOKINETIC POPULATION

The PK population will consist of all treated subjects who have sufficient data to calculate at least one of the PK parameters. However, the PK analysis dataset will exclude data associated with protocol violations and/or major protocol deviations (subject should not have violated any major entry criterion likely to impact the PK analysis and should not have deviated significantly from the protocol between enrollment and successful study completion).

The PK population will be further described in a SAP.

Statistics for demographic and baseline data will be detailed in the SAP.

10.2 STATISTICAL ANALYSES

10.2.1 SAFETY ANALYSES

The clinical laboratory tests, measurements of vital signs, pulse oximetry, ECGs, physical examination, and other safety parameters will be used to perform the safety statistical analysis.

10.2.2 SAFETY ENDPOINTS

The safety endpoints are the frequency, type and severity of AEs, clinical laboratory results, vital signs, ECG, pulse oximetry, physical examination, and neurological assessment findings, and body weight.

10.2.3 SAFETY STATISTICAL METHODOLOGY

All safety data (AEs, clinical laboratory results, vital signs, pulse oximetry and ECGs) will be listed. Safety data will be summarized with descriptive statistics and frequency tables. If requested by the Sponsor and/or SRC additional analysis may be performed.

Statistics for summary of AEs and safety results will be detailed in a SAP.

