|-----------------------------------------------------------|-----------|-----------|---|----|----|-----|---|---|------------------|-------------------------------------------------------------------|-----------------------------------|
| Day | -28 to -2 | -1 | 1 | 2 | 3 | 4 | | 5 | 6 ^{1,2} | | 9-304 |
| Body Weight ¹⁰ | X | Х | | | T | T | T | | Х | | |
| Height | X | | | | | Τ | T | | | | |
| Vein assessment | X | Х | | | T | T | T | 1 | | | |
| вмі | X | | | 34 | | T | T | | | | |
| Physical Examination ¹¹ | X | Х | | | T | T | T | | X | | |
| Neurological assessment ¹² | X | Х | | | T | T | | | X | | |
| Clinical laboratory tests ¹³ | x | х | Х | Х | х | X | | х | Х | | |
| Serology (HIV-1/HIV-2 antibodies, HBsAg and HCVAb) | X | | | | T | T | T | T | | | |
| Urinalysis ¹⁴ | X | Х | Х | х | х | x | | х | Х | | |
| Single 12-lead safety electrocardiogram ¹⁵ | | | Х | Х | T | T | Ť | 1 | | | |
| Triplicate 12-lead safety electrocardiogram ¹⁶ | X | Х | х | Х | х | x | | х | X | | |

AE = adverse event; FSH = follicle stimulating hormone; HIV = Human immunodeficiency virus

¹⁰ Body weight will be assessed at screening. Body weight will be also assessed at admission, and prior to discharge. Weight at admission will used for dosing calculation.

¹¹ A complete physical examination will be performed at screening, admission, and prior to discharge (Day 6).

¹² A complete neurological examination will be performed at screening, admission and prior to discharge (Day 6).

¹³ Clinical laboratory tests (hematology, biochemistry [including lipid profile], coagulation) will be performed at screening, on admission; at 2 hours, 8 hours, and approximately 24 hours post-dose; 48, 72 and 96 hours and before discharge (120 hours).

¹⁴ Spot urinalysis samples will be taken at screening and upon admission. Subsequent small spot urine samples will be obtained pre-dose and at 24, 48, 72, 96, and 120 hours post dose. 24 hour urine Cr will also be measured from each of the 24-hour collection samples as described below under urine and feces.

 $^{^{15}}$ Single recording ECG readings will be taken 1, 3 and 8 minutes post dose.

¹⁶ Triplicate ECG readings to be taken pre-dose (within 2 hours), 20, 40, 60 minutes and 2, 4, 8, 12, 24, 48, 72, 96, 120 hours post dose.

| Assessment | Screening | Admission | Days | | | | | | Post-Treatment Phase Follow-up Phone Call | Subjects to Self-report AEs |

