|---------------------------------------------|-----------|-----------|------|----|---|---|---|------|-------------------------------------------|-----------------------------------|
| Day | -28 to -2 | -1 | 1 | 2 | 3 | 4 | 5 | 61,2 | 8 ³ | 9-304 |
| Alcohol, cotinine and drugs of abuse screen | X | Х | | | Т | Г | Ī | | ĺ | |
| Pregnancy test ¹⁷ | X | Х | | | Τ | Τ | T | Х | | |
| FSH ¹⁸ | х | | | | T | T | T | T | | |
| RVP-001 administration | | | х | K. | T | T | | 1581 | | 1 |
| Injection site monitoring ¹⁹ | | | Х | Х | х | х | х | Х | | |
| Blood PK samples ²⁰ | * | | Х | Х | х | х | х | х | | |
| 7 SM SM I | | х | X | x | х | х | х | X | | |
| Urine and Feces samples ^{21, 22} | | | | | | | | | | f |

AE = adverse event

¹⁷ A highly sensitive urine pregnancy test will be performed at screening for all female subjects. For women of childbearing potential, a highly sensitive urine pregnancy test will also be performed before discharge. A highly sensitive serum pregnancy test will be performed at admission.

¹⁸ Post-menopausal females only.

¹⁹ Injection site monitoring daily until discharge.

²⁰ Blood samples for PK assessment will be collected prior (within 2 hours prior to dose) and at 2, 5, 10, 20, and 30 minutes after the end of the bolus dose and at 1, 2, 4, 8, 12, 24, 48, 72, 96, and 120 hours post-dose (6 mL for each sampling time).

²¹ All urine and feces will be collected for PK and elimination studies and be retained in 24-hour bins. Urine samples will be collected in the following approximate time intervals: -24-0 hours, 0-24 hours, 24-48 hours, 48-72 hours, 72-96 hours, 96-120 hours. Feces samples (entire stool) will be collected in the following approximate time intervals: -24-0 hours, 0-24 hours, 24-48 hours, 48-72 hours, 72-96 hours, 96-120 hours.

²² Pre-dose 24 hour urine collection may be less than 24 hrs depending on time subject enters CSU to time of dosing.

| Assessment | Screening -28 to -2 | Admission | | | Da | ys | | | Post-Treatment Phase Follow-up Phone Call | Subjects to Self-report AEs 9-30 ⁴ |
|----------------------------------|------------------------|-----------|---|---|----|----|---|------|-------------------------------------------|--------------------------------------------------------|
| Day | | -1 | 1 | 2 | 3 | 4 | 5 | 61,2 | 8 ³ | |
| Fluid Monitoring ²³ | | Х | Х | Х | х | х | х | х | | |
| Discharge from clinical site | | | | | T | Г | Г | х | | |

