4.3.3 ASSESSMENT OF POTENTIAL RISKS AND BENEFITS

Mn has a well understood toxicity profile. Known effects from Mn toxicity inform potential safety concerns for the entire class of Mn-containing MRI contrast agents include the possibilities of Mn retention in the brain subsequent to chronic overexposure, hypersensitivity reactions, lowering of seizure threshold, and transient changes in CV function as a consequence of acute overexposure to free Mn2+. To mitigate risk from Mn exposure, RVP-001 was designed to stably chelate Mn2+, to remain intact while in the body, and to be excreted intact. Nonetheless FDA has requested Reveal submit expedited IND safety reports for any reports of seizure, stroke, cerebral venous thrombosis, QTc >480 msec, or QTc increase of 60 msec over baseline, regardless of assessment of causality.

More detailed information about the known and expected benefits and risks and reasonably expected adverse events (AEs) of RVP-001 may be found in the investigator's brochure (IB).

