9.2.6 BIOANALYTICAL SAMPLE COLLECTION AND PROCESSING

Plasma and urine will be analyzed by high performance LC-MS/MS to measure the concentration of intact RVP-001 in order to assess plasma pharmacokinetics at Inotiv. Separate urine and feces samples will be analyzed by ICP-MS for total Mn content to quantify elimination of injected Mn and fractional excretion at Quotient Bioanalytical. Separate plasma and urine samples will be sent to Massachusetts General Hospital for exploratory studies.

A total of 16 blood samples will be drawn from each subject for PK analyses. Venous blood will be collected prior to (within 2 hours prior to dose) and at 2, 5, 10, 20, and 30 minutes after the end of the bolus dose and at 1, 2, 4, 8, 12, 24, 48, 72, 96, and 120 hours post-dose (6 mL for each sampling time).

The acceptable deviations from the nominal blood sampling times are as follows:

- The pre-dose samples will be taken up to 2 hours before dosing
- 0 to 1 hour post-dose samples will be taken within ± 2 minutes of the nominal post-dose sampling time
- 2 to 12 hour post-dose samples will be taken within ± 10 minutes of the nominal post-dose sampling time
- 24 to 120 hour post-dose samples will be taken within ± 30 minutes of the nominal postdose sampling time

The total blood volume withdrawn from each subject will not exceed 550 mL in an 8 week period (based on a representative healthy subject weighing at least 110 pounds). The blood volume taken during the study is presented in Table 5. The number and timing of samples may be amended following any interim PK parameter estimations.

Version 2.0: 9 May 2022 Confidential Page 54

[figure not shown]
Table 5 Estimated Total Blood Volume

| Study Visit | Sample Type | Number of Samples | Sample Volume | Total Volume |
|---------------------------|----------------------------------------------------------------------------------------------------|----------------------|---------------------|--------------|
| Screening | Safety laboratory assessments (biochemistry [including FSH], hematology, coagulation and serology) | 1 | 22.7 mL | 22.7 mL |
| Admission (Day -1) | Safety laboratory assessments (biochemistry [including pregnancy], hematology, and coagulation) | 1 | 15.2 mL | 15.2 mL |
| Day 1 | Safety laboratory assessments (biochemistry, hematology, and coagulation) | 2 | 14.2 mL | 28.4 mL |
| Day 1 to Day 6 | Pharmacokinetic assessments | 16 | 6.0 mL | 96.0 mL |

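### No concentration-QTcF analysis is pre-specified, although QTc is a named concern and most triplicate ECGs share a nominal PK time

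*Combined protocol and SAP*

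**What the plan says.** Section 10.2.3 lists all safety data, ECGs included, and states: "Safety data will be summarized with descriptive statistics and frequency tables". It also allows unspecified further analysis at the request of the sponsor or the Safety Review Committee (SRC), and leaves the safety statistics to a SAP. The supplied text contains no SAP section on ECGs.

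QTc is singled out elsewhere. Section 4.3.3 reports an FDA request for expedited reports of "QTc >480 msec, or QTc increase of 60 msec over baseline, regardless of assessment of causality". Section 9.10.12 repeats it as a class concern: "QTc above 480 msec, or QTc increase of 60 msec over baseline, regardless of assessment of causality". Sections 8.3.1 and 8.3.2 use QTcF thresholds in the subject and cohort stopping rules.

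On data collection, Section 9.2.6 states: "A total of 16 blood samples will be drawn from each subject for PK analyses". Footnote 20 of the Schedule of Activities (Section 3.2) sets the post-dose samples "at 2, 5, 10, 20, and 30 minutes after the end of the bolus dose and at 1, 2, 4, 8, 12, 24, 48" h, continuing to 120 h. Footnote 16 reads "Triplicate ECG readings to be taken pre-dose (within 2 hours), 20, 40, 60 minutes and 2, 4, 8, 12, 24" h, also continuing to 120 h. Footnote 15 gives single ECGs at 1, 3 and 8 min.

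The only formal model in the protocol is the power model for dose proportionality of Cmax and AUC (Section 10.2.10).

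**The concern.** The regulator has asked about QTc, and the trial collects nearly everything needed to relate QTcF to plasma concentration: a pre-dose triplicate, post-dose triplicates at PK times, four dose levels and a concurrent placebo group. The protocol commits only to descriptive displays. If those are read cohort by cohort, each rests on 6 active subjects and uses neither the dose range nor the repeated pairs within a subject.

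The rest of the protocol does not fill this gap. The thresholds in Sections 8.3.1 and 8.3.2 are large individual changes and say little about a modest mean effect. The SRC will try to relate exposure to adverse events (Section 9.12.2), but under Section 9.1.3 an ECG change becomes an adverse event only if clinically significant. A model chosen after unblinding would also carry less weight than one written down beforehand.

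**Working it through.** **Plan's own figure.** There is none. No QTcF SD, precision or power is stated, and Section 10.2.12 says the sample size has no statistical basis. The design arithmetic holds: 4 cohorts × (6 + 2) = 24 active + 8 placebo = 32.

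**Inputs from the protocol.**
- Doses in Table 1 run from 2.0 to 12.0, a ratio of 12/2 = 6.
- Triplicate ECG and PK times coincide nominally at 20 min and 1, 2, 4, 8, 12 and 24 h, which is 7 times within 24 h. They also coincide at 48 to 120 h, which are not used here. The 40-min triplicate has no PK sample.
- That gives 24 × 7 = 168 active pairs and 8 × 7 = 56 placebo pairs.

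**Assumed inputs.**
- Between-/within-subject SD of change in QTcF: 4/4, 6/5 and 7/7 ms. Total SD is √(16+16) = 5.7, √(36+25) = 7.8 and √(49+49) = 9.9 ms.
- Half-life 0.5, 1.5 and 4 h (Section 6.5 says it is unknown in humans).
- Mono-exponential decline with 25% CV, and two-sided 90% intervals.

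**Comparison at one time point.** Half-width = t(0.95, n₁+n₂−2) × SD × √(1/n₁+1/n₂). At SD 7.8 ms:
- 6 vs the 2 in-cohort placebo: 1.943 × 7.81 × 0.8165 = 12.4 ms
- 6 vs 8 pooled placebo: 1.782 × 7.81 × 0.5401 = 7.5 ms
- Mean of 6, not placebo-corrected: 2.015 × 7.81/√6 = 6.4 ms

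**Pooled model.** Change in QTcF = time effect + treatment effect + slope × concentration + random subject effect + error, for all 32 subjects at the 7 times. Half-width = t(0.95, 30) × √(L′(ΣX′V⁻¹X)⁻¹L). L takes the treatment effect plus the slope times the mean top-dose concentration at 20 min. Variances are treated as known, and results are averaged over simulated concentration profiles.

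| Total SD (ms) | 6 vs 2 (ms) | 6 vs 8 (ms) | Model (ms), half-life 0.5 / 1.5 / 4 h | Ratio, 6 vs 2 to model | Ratio, 6 vs 8 to model |
|---|---|---|---|---|---|
| 5.7 | 9.0 | 5.4 | 4.2 / 3.9 / 3.7 | 2.14 / 2.31 / 2.41 | 1.30 / 1.40 / 1.46 |
| 7.8 | 12.4 | 7.5 | 5.7 / 5.4 / 5.2 | 2.16 / 2.30 / 2.38 | 1.31 / 1.40 / 1.44 |
| 9.9 | 15.7 | 9.5 | 7.3 / 6.8 / 6.5 | 2.15 / 2.32 / 2.41 | 1.30 / 1.41 / 1.46 |

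**A second set of assumptions.** With within-subject SD 5 to 9 ms, between-subject SD 4 to 6 ms and half-life 1 to 4 h, total SD runs from √(25+16) = 6.4 to √(81+36) = 10.8 ms. Half-widths are then 10.2 to 17.2 ms (6 vs 2), 6.2 to 10.4 ms (6 vs 8) and about 4.1 to 7.6 ms (model). Comparing like ends, 6.2/4.1 = 1.5 and 10.4/7.6 = 1.4. Over most of this range the 6 vs 8 ratio is about 1.4 to 1.6.

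**Limits on pairing.** Section 9.1.3 allows ±10 min for triplicates in the first 3 h, while Section 9.2.6 allows ±2 min for PK up to 1 h. A nominal 20-min pair can therefore be 12 min apart. Before 20 min, ECGs are single at 1, 3 and 8 min, against PK at 2, 5 and 10 min.

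**The case against.** The strongest case against has five parts.

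1. Section 10.2.3 does not say that ECGs will be summarised by dose and time, it allows further analysis, and it defers detail to a SAP. A reader might infer that descriptive tables are the only ECG analysis planned, or that the paired data are thrown away. The documents support neither. The SAP text is not available, all ECG data are listed, and the model could still be run later. What is missing is pre-specification in the protocol.

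2. A reader might infer that the trial answers its own QTc question badly. The objectives and endpoints (Sections 4.4, 4.5 and 10.2.2) state no mean-QTc estimand. QTc enters as individual thresholds, for which listings and frequency tables are the natural display. This stands: the model supplements those displays and does not replace them.

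3. A reader might infer that the descriptive approach is much less precise. That fits only the comparison with 2 in-cohort placebo, which the protocol nowhere specifies. Against pooled placebo the gain is moderate. Against the uncorrected mean of 6 it is about 6.4/5.4 = 1.2, though that mean is not placebo-corrected. In a simpler regression on dose at SD 8 ms with no true effect, the chance that the upper 90% bound lies below an illustrative 10 ms (a bound not taken from the documents) is 0.79, against 0.70 for 6 vs 8 and 0.39 for 6 vs 2.

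4. A modest effect may still not be separated from zero with a half-width of about 4 to 7.6 ms. This also stands; the gain is in precision, with no guarantee of detection.

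5. The calculation favours the model: known variances, mono-exponential decline (Table 8 expects a distribution phase), a linear effect without delay, and exact pairing. The bolus takes 5 to 15 s (Section 7.1.2), so exposure peaks well before 20 min.

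These points narrow the claim. They do not remove the case for a short pre-specified exploratory model.

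**Conclusion.** The point holds as a low-cost improvement. The protocol pre-specifies no concentration-QTcF analysis, although QTc is a named concern and the paired data will exist. Intervals for a placebo-corrected effect at the top-dose 20-min concentration would be roughly 1.3 to 1.6 times as wide from 6 active against 8 pooled placebo as from the pooled model, and over 2 times as wide against the 2 in-cohort placebo. The direction is the same in every scenario tried. The size rests on assumed SDs, half-lives and PK shape, on a linear undelayed effect, and on close pairing. It applies from 20 min onward and says nothing about peak exposure. If the SAP already contains such a model, only the protocol cross-reference is missing.

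**What to change.** In Section 10.2.3 and the SAP, before unblinding, pre-specify one exploratory linear mixed model:

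- **Response and terms:** change from pre-dose QTcF on plasma RVP-001 concentration, with treatment, nominal time, baseline QTcF and a random subject effect.
- **Data:** all active subjects and all placebo subjects pooled over cohorts, with placebo concentration set to 0.
- **Pairing:** by actual ECG and PK times, either interpolating concentration or excluding pairs beyond a stated gap.
- **Checks:** linearity and delayed effect.
- **Report:** predicted placebo-corrected effects with 90% CI, only over the concentrations seen at the paired times (20 min onward).

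Keep the listings and threshold tables. Show the single 1, 3 and 8 min ECGs descriptively, and state that the model does not cover peak exposure.

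The cost is a paragraph of text and a little more analysis, with no new samples, visits or subjects. The remaining weakness is limited information about the first minutes after the bolus.
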